### 3. ENDPOINTS AND BASELINE VARIABLES: DEFINITIONS AND CONVENTIONS

#### 3.1. Primary Endpoints

- The proportion of sentinel-cohort subjects with clinical laboratory abnormalities following investigational product (IP) administration at the 1-week follow-up visit.
- The proportion of subjects reporting prompted local reactions within 14 days following IP administration (redness, swelling and pain at the injection site).
- The proportion of subjects reporting prompted systemic events within 14 days following IP administration (fever, nausea/vomiting, diarrhea, headache, fatigue, muscle pain, and joint pain).
- The proportion of subjects reporting AEs within 1 month following IP administration.
- The proportion of subjects reporting MAEs and SAEs within 6 months following IP administration.

### 3.2. Secondary Endpoint

- GBS serotype-specific IgG geometric mean concentrations (GMCs) measured 1 month after vaccination.

CCI

### 3.4. Baseline Variables

Day 1 is defined as the day of vaccination and start of the reporting period for local and systemic reactions in the e-diary.

#### Sentinel Cohort Subjects

Laboratory data will be collected for sentinel cohort subjects only. Data is collected during the screening visit, Visit 0 (-14 to -2 days prior to vaccination) and will be considered baseline data. For subjects with a rescreening visit, the rescreening laboratory results will be considered as the baseline data.

Day 1 is considered the baseline visit for the following assessments: Immunogenicity, [CCI] and vital signs.

#### Expanded Cohort Subjects

Day 1 is considered the baseline visit for the following assessments: Immunogenicity, [CCI] and vital signs.

#### **3.4.1. Demographic, Medical History and Baseline Characteristics**

Demographic variables collected include gender, race, ethnicity and date of birth. Age at time of vaccination (in years) will be derived based on birthday. For example, if the vaccination date is one day before the subject's 19th birthday, the subject is 18 years old.

Medical history of clinical significance will be collected and categorized according to the current version (at time of reporting) of the Medical Dictionary of Regulatory Activities (MedDRA).

[CCI]  
[Redacted text block]

#### **3.6. Safety Endpoints**

##### **3.6.1. Adverse Events**

The time period for reporting AEs for all subjects is from the time the informed consent is signed to 1 month follow-up visit (Visit 4). For all subjects, only MAEs and SAEs will be collected at Visit 5 (3 month) and Visit 6 (6 month) follow-up visits. Additionally, AEs occurring up to 48 hours after Visit 5 (3 month) and Visit 6 (6 month) that are related to study procedure (e.g., blood draw) will be collected for all subjects.

All AEs are collected on the case report form (CRF) and will be categorized according to the current version (at time of reporting) of the Medical Dictionary of Regulatory Activities (MedDRA).

An immediate AE is defined as any AE that occurred within the first 30 minutes after IP (see Section 7.8.2 Immediate Adverse Events of the protocol).

A MAE is defined as a nonserious AE that results in an evaluation at a medical facility.

[Redacted text block]

AEs will be captured and reported in accordance with Pfizer reporting standards.

A 3-tier approach will be used to summarize AEs. Under this approach, AEs are classified into 1 of 3 tiers. Different analyses may be performed for different tiers.

- Tier-1 events: These are prespecified events of clinical importance and, if any, are maintained in a list in the product's Safety Review Plan. There are no pre-identified tier-1 events for this study.
- Tier-2 events: These are events that are not tier-1 but are "common." A MedDRA preferred term (PT) is defined as a tier-2 event if there are 4 or more subjects in at least one vaccine group.
- Tier-3 events: These are events that are neither tier-1 nor tier-2 events.

### **3.6.2. Reactogenicity Data**

Reactogenicity data are solicited AEs collected using e-diary, during Days 1-14, starting on the day of the vaccination [Day 1 (Visit 1)] following the IP administration. The reactogenicity data will include local reactions (pain at injection site, erythema/redness, and induration/swelling), systemic events (fever, nausea/vomiting, diarrhea, headache, fatigue, muscle pain, and joint pain) and the use of antipyretic medication. Clinical to provide any errors noted on e-diary and specific instructions on handling them.

#### **3.6.2.1. Local Reactions**

Local reactions reported in the e-diary are pain at injection site, erythema/redness, and induration/swelling.

##### Presence of Local Reactions (Proportion of Subjects Reporting)

The subject will record the presence or absence of pain at injection site in the e-diary as 'Mild', 'Moderate', 'Severe' or 'None'. The presence or absence of redness or swelling to be recorded as 'Yes' or 'No'. Additionally, if redness or swelling is present, then the subject will use a caliper to measure the largest diameter and record the measurement rounded up to the nearest whole number. Caliper units are converted to centimeters according to 1 caliper unit = 0.5 centimeters.

Only an investigator is able to classify a subject's local reaction as Grade 4, after physical examination of the subject or documentation from another medically qualified source (e.g., emergency room or hospital record), or, in the case of pain at the injection site only, telephone contact with the subject. If a subject experiences a Grade 4 local reaction, it will be captured in the unplanned visit CRF page. A severe local reaction entry in the e-diary that later is assessed as Grade 4 will be treated as Grade 4 for analyses.

The presence or absence of each local reaction on a given day is defined as follows:

= missing if value is missing on a given day;

= 'Yes', if the subject reports the reaction as 'Yes' for redness or swelling **or** 'Mild', 'Moderate' or 'Severe' or 'Grade 4' for pain at injection site on a given day;

= 'No' if the subject reports the reaction as 'No' for redness or swelling **or** 'None' for pain at injection site on a given day.

For each local reaction, the derivation of whether or not the specific reaction occurred on "any Day 1-14" will be made. The derivation of this variable is given in Table 3 below.

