### 7.5.1. Subject Electronic Diary

The subject will be asked to monitor and record local reactions, systemic events, fever, and antipyretics/pain medication used to treat symptoms, each evening for 14 days following vaccination (Day 1 through Day 14, where Day 1 is the day of vaccination) on a system that uses a personal digital assistant (PDA) or other technology. This system, hereafter referred to as the subject's e-diary, allows recording of these assessments only within a fixed time window, thus providing the accurate representation of the subject's experience at that time. Data on local reactions, systemic events, and antipyretics/pain medication used to treat symptoms reported on the e-diary will be transferred electronically to the e-diary vendor, where they will be available for review by investigators, their qualified designees, and sponsor staff at all times via an internet-based portal. At intervals agreed to by the vendor and Pfizer, these data will be transferred electronically to Pfizer for analysis and reporting. These data do not need to be reported by the investigator in the CRF. However, if a subject withdraws because of prompted events reported in the e-diary, the event(s) should be

recorded on the AE page of the CRF, regardless of whether the investigator considers the event(s) to be clinically significant.

Investigators (or appropriately qualified designee) are required to review the e-diary data online to evaluate subject compliance and as part of the ongoing safety review (see Stopping Rules in [Section 7.7](#)).

The investigator or designee must contact the subject in order to obtain stop dates for any reactions ongoing on the last day that the e-diary was completed. The stop dates should be documented in the source documents and the information entered in the CRF by Visit 4.

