**Table 3. Derived Variables for Each Local Reaction**

Variable a	Yes (1)	No (0)	Missing (.)
Any Day 1-14	Subject reports the reaction as 'Yes' on any Day 1-14	Subject reports the reaction as 'No' on all 14 days or as a combination of 'No' and missing on all 14 days.	Subject reports the reaction as missing on all 14 days.

a. The variable will be defined for each of the 3 local reactions.

For any local reaction on any day, a similar definition can be applied as given in Table 4 below.

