**Table 4. Derived Variables for Any Local Reaction**

Variable	Yes (1)	No (0)	Missing (.)
Any Day 1-14	Subject reports any local reaction as 'Yes' on any day during Days 1-14	Subject reports the reaction as 'No' on all 14 days or as a combination of 'No' and missing on all 14 days for all 3 local reactions.	Subject reports all of the local reactions as missing on all 14 days.

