#### **3.6.2.2. Systemic Events**

Systemic events reported via e-diary are: fever, nausea/vomiting, diarrhea, headache, fatigue, muscle pain, and joint pain. The highest temperature for each day for 14 days after vaccination to be recorded in the e-diary. The protocol defines fever as an oral temperature  $\geq 100.4^{\circ}\text{F}$  ( $38.0^{\circ}\text{C}$ ). For ongoing fever on Day 14, the stop date will be recorded in the CRF. Additionally, the subject to document the presence or absence of remaining systemic events in the e-diary as ‘Mild’, ‘Moderate’, ‘Severe’ or ‘None’. Subjects to be asked to assess severity of each event according to the [Table 6](#) below. Only an investigator is able to classify a subject’s systemic event as Grade 4, after physical examination of the subject or documentation from another medically qualified source (e.g., emergency room or hospital record), or telephone contact with the subject. If a subject experiences a Grade 4 systemic event, it will be captured under the unplanned visit CRF page. A severe systemic event entry in the e-diary that later is assessed as Grade 4 will be treated as Grade 4 for analyses.

Any temperature recorded as  $<95.0^{\circ}\text{F}$  ( $35.0^{\circ}\text{C}$ ) or  $>107.6^{\circ}\text{F}$  ( $42.0^{\circ}\text{C}$ ) will be treated as data entry errors and excluded from the analyses. For reporting purposes, fever will be analyzed using the following temperature ranges:

- $100.4^{\circ}\text{F}$  to  $101.1^{\circ}\text{F}$  ( $38.0^{\circ}\text{C}$  to  $38.4^{\circ}\text{C}$ )

- 101.2°F to 102.0°F (38.5°C to 38.9°C)
- 102.1°F to 104.0°F (39.0°C to 40.0°C)
- >104.0°F (>40.0°C)

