4. Presence or absence of any systemic event on “any Day 1-14” after vaccination.
5. Duration of each systemic event after vaccination.
6. Onset day of each systemic event after vaccination.
7. Onset day of any systemic event after vaccination.

The derivation of these variables is similar to the derivation of the variables for local reactions ([Section 3.6.2.1](#)). Any systemic event includes fever, nausea/vomiting, diarrhea, headache, fatigue/tiredness, muscle pain or joint pain.

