## 3.7. Study Conduct

### 3.7.1. E-diary Completion

On a specific day, the subject is expected to complete all the questions [the 3 local reactions, the 7 systemic events (including fever), and the use of antipyretic medication] in e-diary. In that case, e-diary will be transmitted and considered as complete. The data could be missing in the e-diary for a specific day, in which case it will not be transmitted and considered incomplete. All the data reported on the e-diary will be transferred electronically to the e-diary vendor.

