#### 5.3.2.1. Reactogenicity Data

For derived variables based on reactogenicity data, if any day of the 14-day e-diary is available, the ‘any day 1-14’ data will be considered as non-missing.

The reactogenicity data are collected through e-diary, which does not allow subjects to skip the question. Therefore, for a specific day, as long as the e-diary data is transferred for that day, all of the reactogenicity data for the subject on that day is non-missing. No missing reactogenicity data will be imputed other than what is described in [Section 3.6.2](#).

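### The SAP's only explicit route for an investigator-assessed Grade 4 prompted event into the severity tables starts from a 'severe' e-diary entry, so a diary with only 'No'/'None' and missing days is, read literally, coded as no event

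*SAP*

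**What the plan says.** SAP 3.6.2.1 and 3.6.2.2 reserve Grade 4 for the investigator. The basis is a physical examination or a document from another medical source; a telephone contact is enough for injection-site pain and for systemic events. The footnotes to SAP Tables 5 and 6 add that the diary does not collect Grade 4 and that it goes onto the CRF as an AE. The text of both sections also names the unplanned-visit CRF page.

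One sentence in each section connects the investigator's grade to the analysis:

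- Local: "A severe local reaction entry in the e-diary that later is assessed as Grade 4 will be treated as Grade 4 for analyses".
- Systemic: "A severe systemic event entry in the e-diary that later is assessed as Grade 4 will be treated as Grade 4 for analyses".

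The variables are otherwise built from diary days. In Table 3 a reaction is 'No' over Days 1-14 if every day is 'No', or if the days are a mix of 'No' "and missing on all 14 days". Table 4 applies the same logic to any local reaction ("and missing on all 14 days for all 3 local reactions"). The maximum-severity rule gives 0 for the same patterns and gives missing only when all 14 days are missing. For systemic events, "The derivation of these variables is similar to the derivation of the variables for local reactions". SAP 5.3.2.1 closes the list: "No missing reactogenicity data will be imputed other than what is described in" Section 3.6.2.

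Maximum severity is the analysed variable for both prompted-event primary endpoints, and the tables in SAP 6.1.2.1 and 6.1.3.1 include a Grade 4 row.

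**The concern.** Grade 4 reaches the trial database through the CRF, but the severity tables draw it in only where the subject has already entered 'severe' in the diary. Most Grade 4 definitions in SAP Tables 5 and 6 are an emergency room visit or a hospital admission, and either could cost the subject that evening's diary. Both documents foresee gaps. SAP 3.7.1 says: "The data could be missing in the e-diary for a specific day, in which case it will not be transmitted and considered incomplete". Protocol 7.5.1 says the diary "allows recording of these assessments only within a fixed time window". The length of that window is not given, so whether a missed evening could be filled in afterwards is unknown. For redness and swelling, Grade 4 is defined by necrosis (or exfoliative dermatitis for redness) and not by diameter, so a 'severe' diary measurement is not a precondition for Grade 4.

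At stake is whether a first-in-human study with safety as its primary objective could print an empty Grade 4 row in a primary reactogenicity table while its AE table shows the event.

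**Working it through.** The plan gives no figure to reproduce on this point. The check has two parts: a literal trace of the SAP 3.6.2 derivation, and the effect of one affected subject on a table row.

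**Trace.** Take a subject with an investigator-confirmed Grade 4 event. Apply the rules in order: a 'severe' entry becomes Grade 4; all 14 days missing gives missing; only 'No'/'None', with or without missing days, gives 0; otherwise take the highest grade among the diary values.

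| Diary for that event, Days 1-14 | Literal maximum severity |
|---|---|
| 1 day 'Severe', 13 missing | 4 |
| 14 days 'None' | 0 |
| 13 days 'None', 1 missing | 0 |
| 2 days 'None', 12 missing | 0 |
| 14 missing | missing |

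Only the first diary carries the Grade 4 through. The next three give 0, and presence over Days 1-14 is 'No' by Table 3. The last is missing, not 'no event', so the problem needs at least one transmitted 'No'/'None' day.

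**How firm the trace is, by event type.**

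- *Redness and swelling.* The day-level presence rule in SAP 3.6.2.1 accepts only a reported 'Yes' or 'No'. It has no Grade 4 value, so nothing in the section competes with the literal result.
- *Pain and the non-fever systemic events.* The day-level rules list 'Grade 4' among the values that count as 'Yes'. They present it as something the subject reports, yet the table footnotes say the diary does not collect it. One reading is that the value exists only because 'severe' entries are upgraded. Another is that investigator-assessed values were meant to enter directly. The SAP does not choose between them.
- *Fever.* It has temperature bands and no Grade 4 definition, so it is unaffected.

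**Effect of one affected subject.** Protocol 3.3 plans 52 subjects in each of six GBS6 groups and 51 on placebo (6 × 52 + 51 = 363, the planned total). The interval is Clopper-Pearson, as in SAP 5.2.1. For r = 0 the upper limit is 1 − 0.025^(1/n). For r = 1 the lower limit is 1 − 0.975^(1/n), and the upper limit is the 0.975 quantile of a beta(2, n − 1) distribution.

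| Group | Event counted | Event coded 0 |
|---|---|---|
| GBS6, n = 52 | 1/52 = 1.9% (0.05 to 10.3) | 0/52 = 0% (0 to 6.8) |
| Placebo, n = 51 | 1/51 = 2.0% (0.05 to 10.4) | 0/51 = 0% (0 to 7.0) |

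The documents give neither a Grade 4 rate nor the share of such events with this diary pattern. A probability that the trial meets the case would therefore rest wholly on assumed inputs, and none is offered.

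**The case against.** The best defence is that the quoted sentence gives one condition under which Grade 4 applies and does not say it is the only one. The day-level lists for pain and systemic events already contain a Grade 4 value that no subject can enter, which suggests that investigator assessments were meant to count. The SAP's own change table (Table 1) records that Grade 4 local reactions and systemic events are derived from the investigator's assessment, with no mention of a diary entry. SAP Section 2 keeps programming rules in a separate document, and SAP 3.6.2 leaves the handling of diary errors to clinical instruction; either might cover the case. Protocol 7.8.1 sends events reported outside the diary to AE reporting, so showing such an event only as an AE is a defensible presentation.

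Much of this stands. A reader might infer that the SAP definitely codes every such event as absent. For pain and the non-fever systemic events the documents do not support that. The change table is evidence of intent; it does not supply a rule, and the difference from the body is not itself an error. The separate programming rules may settle the matter, but the SAP defines these primary variables in detail and its stated result for this diary pattern is 0. The presentation argument is weakened by the Grade 4 row itself, which can be filled only from CRF data.

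Three other inferences go too far. The event is not lost from safety reporting: it is recorded as an AE and counts in the 1-month AE endpoint (SAP 6.1.4.1). A Grade 4 event with only a mild or moderate diary entry might be under-graded, but that turns on whether the 'highest grade' rule takes in the CRF grade, which the SAP does not say. Naming both the unplanned-visit page and the AE record is not a contradiction, since an event can be on both; that some Grade 4 events would be on the AE page alone is conjecture.

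**Conclusion.** The point holds in a limited form. The only explicit carry-over rule starts from a 'severe' diary entry, while the rules for 'No' plus missing days give an explicit result of no event. For redness and swelling the literal derivation is wrong for a confirmed Grade 4 event with that diary pattern. For pain and the non-fever systemic events the text is internally inconsistent.

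One affected subject shifts a Grade 4 row by 1.9 percentage points in a GBS6 group and 2.0 in placebo, and changes the upper confidence limit from 10.3% to 6.8% or from 10.4% to 7.0%. These figures assume the planned group sizes with every subject in the denominator. The case is likely rare. The effect is confined to the reactogenicity outputs: the AE analyses are unchanged, and SAP 5.1 plans no hypothesis test or statistical decision rule. This is a minor clarification, worth making because it costs almost nothing.

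**What to change.** In SAP 3.6.2.1 and 3.6.2.2, state that any prompted event with a Grade 4 definition in Table 5 or Table 6, with onset on Days 1-14 and assessed by the investigator as Grade 4, does the following whatever the diary holds:

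- sets presence to 'Yes' on the day or days recorded on the CRF;
- counts towards the onset day;
- sets presence over Days 1-14 to 'Yes', for the specific event and for any local reaction or any systemic event;
- sets maximum severity to Grade 4.

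Name the Grade 4 record on the unplanned-visit and AE CRF pages as the source. For a subject with no transmitted diary day, footnote the event in the same table and leave the denominator unchanged, so that inclusion does not depend on the outcome. If the programming rules already do this, moving the statement into the SAP is enough.

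The cost is a few sentences, a merge of two CRF sources already collected, and a footnote. It needs no new data and does not alter the AE analyses or the grading definitions.

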**Table 3. Derived Variables for Each Local Reaction**

Variable a	Yes (1)	No (0)	Missing (.)
Any Day 1-14	Subject reports the reaction as 'Yes' on any Day 1-14	Subject reports the reaction as 'No' on all 14 days or as a combination of 'No' and missing on all 14 days.	Subject reports the reaction as missing on all 14 days.

a. The variable will be defined for each of the 3 local reactions.

For any local reaction on any day, a similar definition can be applied as given in Table 4 below.

**Table 4. Derived Variables for Any Local Reaction**

Variable	Yes (1)	No (0)	Missing (.)
Any Day 1-14	Subject reports any local reaction as 'Yes' on any day during Days 1-14	Subject reports the reaction as 'No' on all 14 days or as a combination of 'No' and missing on all 14 days for all 3 local reactions.	Subject reports all of the local reactions as missing on all 14 days.

### Grading Scale for Local Reactions

The grading of local reactions is listed below in Table 5.

**Table 5. Local Reactions Grading Scale**

	Mild (Grade 1)	Moderate (Grade 2)	Severe (Grade 3)a	Grade 4b
Pain at injection site	Does not interfere with activity	Repeated use of non-narcotic pain reliever > 24 hours or interferes with activity	Any use of narcotic pain reliever or prevents daily activity c	Emergency room visit or hospitalization
Erythema/Redness	2.5 cm to 5.0 cm (5 to 10 caliper units)	>5.0 cm to 10.0 cm (11 to 20 caliper units)	>10 cm (≥21 caliper units)	Necrosis or exfoliative dermatitis
Induration/Swelling	2.5 cm to 5.0 cm (5 to 10 caliper units)	>5.0 cm to 10.0 cm (11 to 20 caliper units)	>10 cm (≥21 caliper units)	Necrosis

- Subjects experiencing ≥ Grade 3 local reactions are to be seen by the study site.
- Grade 4 assessment should be made by the investigator; a Grade 4 event will not be collected in the e-diary but will be recorded as an AE on the CRF.
- Prevents daily activity, i.e., results in missed days of work or school or is otherwise incapacitating, or includes use of narcotics for analgesia.

### Maximum Severity for Local Reactions

The maximum severity (highest grading) of each local reaction within 14 days of vaccination will be derived. The maximum severity will be derived as follows:

= missing if values are missing for all Days 1-14;

= 0, if the subject reports all reactions as ‘No’ or a combination of missing and “No” for all Days 1-14;

= *highest grade* (maximum severity) within 14 days of vaccination, if the answer is not ‘No’ for at least 1 day.

